A Phase 1 Study to Evaluate the Pharmacokinetics and Tolerability of a Single Subcutaneous Dose of Tralokinumab When Delivered as a 2 mL Injection at Different Flow Rates to Healthy Volunteers

Sponsor Protocol Number: D2210000011

Application Number:	IND 100,702
Investigational Product:	Tralokinumab (CAT-354)
Sponsor:	
Project Director:	

Contract Research Organization:

Protocol History, Date: Original Protocol,

PROTOCOL SYNOPSIS

TITLE

A Phase 1 Study to Evaluate the Pharmacokinetics and Tolerability of a Single Subcutaneous Dose of Tralokinumab When Delivered as a 2 mL Injection at Different Flow Rates to Healthy Volunteers

HYPOTHESES

Primary Hypothesis: The primary hypothesis to be tested is that delivery of a single 2 mL subcutaneous (SC) injection of 300 mg tralokinumab at different flow rates has no significant impact on its pharmacokinetic (PK) profile as compared to delivery as 2×1 mL injections.

Secondary Hypotheses

- 1. Increasing the volume of injection of tralokinumab from 1 mL to 2 mL reduces the tolerability of the injection at a given flow rate (as measured by pain, pruritus, and local injection-site reactions)
- 2. Decreasing the flow rate of injection of tralokinumab improves the tolerability of the injection (as measured by pain, pruritus, and local injection site reactions)

OBJECTIVES

Primary Objective: To evaluate the PK profile of a single SC dose of 300 mg tralokinumab when delivered as a 2 mL injection at different flow rates to healthy adult volunteers

Secondary Objectives

- 1. To determine the local tolerability and overall safety profile of a single SC dose of 300 mg tralokinumab when delivered as a 2 mL injection at different flow rates
- 2. To determine the immunogenicity profile of a single SC dose of 300 mg tralokinumab when delivered as a 2 mL injection at different flow rates

Exploratory Objectives

To determine the effect of a single SC dose of 300 mg tralokinumab when delivered as a single 2 mL injection at different flow rates in healthy volunteers on biomarkers relevant to the mechanism of action of tralokinumab

STUDY ENDPOINTS

Primary Endpoint: The primary endpoint is the PK profile of tralokinumab.

Secondary Endpoints

- 1. Local injection site pain intensity and injection site pruritus post-injection
- 2. Local injection site reactions (eg, erythema, bleeding, rash, etc) post-injection
- 3. Presence of fluid leakage immediately post-injection
- 4. Incidence of treatment-emergent adverse events including clinically significant changes in vital signs, physical examinations, and laboratory parameters
- 5. Presence of anti-drug antibodies to tralokinumab

Exploratory Endpoints

Assessment of biomarkers (including periostin and dipeptidyl peptidase-4) relevant to the mechanism of action of tralokinumab

STUDY DESIGN

Wisenfeld-Hallin, 2005; Paller et al, 2009), randomization

will be stratified by gender. A minimum of 5 males and 5 females will be randomized to each cohort; the additional subjects may be of either sex. All injections will be administered SC in the abdomen using a syringe pump and SC insertion set at the following flow rates:

• Cohort 1: 2×1 mL SC injections, with each injection delivered at a rate of 6 mL/minute (min)

- Cohort 2: 1×2 mL SC injection delivered at a rate of 12 mL/min
- Cohort 3: 1×2 mL SC injection delivered at a rate of 2 mL/min
- Cohort 4: 1×2 mL SC injection delivered at a rate of 0.167 mL/min

A screening visit will be performed within 21 days prior to dosing. Subjects will be admitted to the study unit on Day -1. Following administration of 300 mg tralokinumab on Day 1, subjects will be followed up for 57 days for safety, tolerability, immunogenicity, and PK sampling.

Subjects will be in this study for up to 79 days, which includes a screening/consent period of up to 21 days, a 1-day treatment period, and a 57-day post-treatment follow-up period.

TARGET SUBJECT POPULATION

The study population will be healthy male and female volunteers ages 19-65 years.

INVESTIGATIONAL PRODUCT, DOSAGE, AND MODE OF ADMINISTRATION

A total of 60 subjects (15 subjects each cohort) will be assigned to 1 of 4 cohorts to receive a single dose of 300 mg tralokinumab SC at the following flow rates:

- Cohort 1: 300 mg tralokinumab as 2 × 1 mL SC injections, with each injection administered at a flow rate of 6 mL/min
- Cohort 2: 300 mg tralokinumab as a 1×2 mL SC injection administered at a flow rate of 12 mL/min
- Cohort 3: 300 mg tralokinumab as a 1×2 mL SC injection administered at a flow rate of 2 mL/min
- Cohort 4: 300 mg tralokinumab as a 1 × 2 mL SC injection administered at a flow rate of 0.167 mL/min

All injections will be administered SC in the abdomen using a syringe pump and SC insertion set.

STATISTICAL ANALYSIS PLAN

Analysis Populations

The PK population is defined as all subjects in the as-treated population with at least one detectable tralokinumab serum concentration and for whom the PK parameters can be adequately estimated.

The as-treated population includes all subjects who receive any amount of investigational product. Subjects will be included in the as-treated population according to the injection flow rate received even if different from that to which the subject was randomized. Demographics, safety and tolerability endpoints, and biomarkers will be summarized based on the as-treated population.

Planned Analysis

Using the serum concentrations of tralokinumab, the PK parameters will be analyzed using noncompartmental models. Given the small sample size and the exploratory nature of the study, mainly descriptive statistics will be provided for the secondary and exploratory endpoints by cohort over time. Categorical data will be summarized by the number and percentage of subjects in each category. Continuous variables will be summarized by mean, standard deviation, median, and range. The distribution of pain intensity scores will be examined and the between-cohort difference will be explored.

Sample Size/Power Calculation

The number of subjects planned for this study is based on the number required to obtain adequate PK data while exposing as few healthy volunteer subjects as possible to tralokinumab and procedures. A total of 15 subjects per treatment arm is considered sufficient to detect an approximately 1.5-fold difference in PK parameters between cohorts and will provide exploratory information regarding local tolerability.

TABLE OF CONTENTS

PRO	DTOCC	DL SYNOPSIS	2
1	INT	RODUCTION	10
	1.1	Disease Background	10
	1.2	Tralokinumab Background	11
	1.3	Summary of Nonclinical Experience	11
	1.4	Summary of Clinical Experience	11
	1.5	Rationale for Conducting the Study	13
	1.6	Research Hypotheses	14
		1.6.1Primary Hypothesis	14
		1.6.2Secondary Hypotheses	15
2	OBJ	ECTIVES	15
	2.1	Objectives	15
		2.1.1Primary Objective	15
		2.1.2Secondary Objectives	15
		2.1.3Exploratory Objectives	15
	2.2	Study Endpoints	15
		2.2.1Primary Endpoint	15
		2.2.2Secondary Endpoint(s)	15
		2.2.3Exploratory Endpoint(s)	16
3	STU	DY DESIGN	16
	3.1	Description of the Study	16
		3.1.10verview 16	
		3.1.2Treatment Regimen	18
	3.2	Study Design and Dose Rationale	18
		3.2.1Dose Rationale	18
		3.2.2Rationale for Study Population	18
		3.2.3Rationale for Endpoints	19
4	MA	FERIALS AND METHODS	20
	4.1	Subjects	20

Appendix 6	Additional Safety Guidance	73
Appendix 7	National Institute of Allergy and Infectious Diseases and Food Aller	rgy
	and Anaphylaxis Network Guidance for Anaphylaxis Diagnosis	76
Appendix 8	Signs and Symptoms and Management of Acute Anaphylaxis	77

List of Abbreviations

Abbreviation or Specialized Term	Definition		
ADA	anti-drug antibodies		
AE	adverse event		
AESI	adverse event of special interest		
AHR	airway hyper-responsiveness		
ALT	alanine transaminase		
AST	aspartate transaminase		
AUC	area under the serum concentration-time curve		
AUC _{0-~}	area under the serum concentration-time curve from zero to infinity		
AUC _{0-t}	area under the serum concentration-time curve to last observation		
BD	Becton, Dickinson, and Company		
BP	blood pressure		
CAT-354	tralokinumab		
CL/F	apparent systemic clearance		
C _{max}	maximum concentration		
CV	coefficient of variation		
DNA	deoxyribonucleic acid		
DPP-4	dipeptidyl peptidase-4		
ECG	electrocardiogram		
eCRF	electronic case report form		
FEV ₁	forced expiratory volume in one second		
FSH	follicle-stimulating hormone		
G	gauge		
GCP	Good Clinical Practice		
GINA	Global Initiative for Asthma		
GMP	Good Manufacturing Practice		
HIV	human immunodeficiency virus		
IB	Investigator's Brochure		
ICH	International Conference on Harmonisation		
ICS	inhaled corticosteroids		
IEC	Independent Ethics Committee		
IgG4	immunoglobulin G4		
IgE/G	immunoglobulin E/G		
IL-13	interleukin-13		
IRB	Institutional Review Board		
IV	intravenous		
LABA	long-acting β2-agonist		
mAb	monoclonal antibody		
min	minute(s)		

Abbreviation or Specialized Term	Definition	
MSRB	MedImmune Safety Review Board	
PEF	peak expiratory flow	
РК	pharmacokinetic(s)	
Q2W	every 2 weeks	
Q4W	every 4 weeks	
SABA	short-acting β2-agonist	
SAE	serious adverse event	
SAP	statistical analysis plan	
SC	subcutaneous	
SD	standard deviation	
SID	subject identification	
SUSAR	suspected unexpected serious adverse reaction	
t _{1/2}	half-life	
ТВ	tuberculosis	
TEAE	treatment-emergent adverse event	
TESAE	treatment-emergent serious adverse event	
Th2	T-helper-2	
T _{max}	time to maximum concentration	
ULN	upper limit of normal	
USA	United States of America	
VAS	visual analogue scale	
Vz/F	apparent terminal-phase volume of distribution	
WBDC	Web Based Data Capture	

1 INTRODUCTION

1.1 Disease Background

Asthma is a chronic inflammatory disease in the airways characterized by bronchial hyperactivity and reversible limitation of airflow that causes wheezing, shortness of breath, cough, and chest tightness. International treatment guidelines such as Global Initiative for Asthma (GINA; GINA, 2012) recommend inhaled corticosteroids (ICS) as first-line therapy for persistent asthma. For those patients that are symptomatic and on ICS alone, the addition of a long-acting β 2-agonist (LABA) is the current treatment of choice. However, there are a number of asthmatic patients who are still symptomatic despite treatment with ICS and LABA combinations (Rabe et al, 2004). Treatment options then include the addition of other controller therapies including leukotriene antagonists, theophylline, and oral glucocorticosteroids. Xolair® (omalizumab) may be suitable for a subgroup of patients with elevated serum immunoglobulin E (IgE) levels.

Approximately 5% to 10% of asthma patients have severe asthma, which may be inadequately controlled by ICS and LABA combinations together with additional controller therapies (Brightling et al, 2008). These patients are at risk of asthma exacerbations (Tough et al, 1998; Turner et al, 1998; Chipps et al, 2012), have the greatest medical need among the asthmatic population today, and represent the greatest economic cost (> 50% of total asthma-related health care costs; Antonicelli et al, 2004; Barnes et al, 1996; Accordini et al, 2006). Thus, there is a clear medical need for patients with severe asthma who are unable to gain complete asthma control using currently available therapies.

Interleukin-13 (IL-13) is a member of the interleukin family of cytokines and is secreted predominantly by CD4+ T-helper-2 (Th2) cells. Interleukin-13 receptors are expressed on a number of cell types including key cells involved in asthma (Hershey, 2003), There is considerable evidence that IL-13 is a key mediator in the pathogenesis of established asthmatic disease and may have a number of effects including inflammation, airway hyper-responsiveness (AHR), fibrosis, and increased mucous production. Elevated IL-13 levels have been identified in the sputum of a proportion of patients with asthma including those with severe disease treated with systemic corticosteroids (Saha et al, 2008). Therefore, a significant role for IL-13 in asthma can be expected. Coupled with the evidence of a relationship between IL-13 expression and disease severity in patients, neutralization of IL-13 by tralokinumab is a credible approach to the treatment of asthma.

Further information on the role of IL-13 in asthma, and a full list of citations, can be found in the Investigator's Brochure (IB) for tralokinumab.

1.2 Tralokinumab Background

Tralokinumab is briefly described below. Refer to the current IB for details.

Tralokinumab is a human recombinant monoclonal antibody (mAb) of the immunoglobulin G4 (IgG4) subclass that specifically binds human IL-13, blocking interactions with the IL-13 receptors. MedImmune has used phage display and recombinant deoxyribonucleic acid (DNA) technologies to isolate a human mAb fragment with specificity for human IL-13 that demonstrated potent in vitro neutralization of IL-13 activity. Tralokinumab resulted from reformatting the precursor as a human IgG4 isotype (CAT-354) by recombinant DNA technology.

1.3 Summary of Nonclinical Experience

In vitro assays have demonstrated that tralokinumab is a potent inhibitor of IL-13-induced effects in a range of cells relevant to asthma. In vivo, in a mouse model of human IL-13-induced lung inflammation and AHR, tralokinumab effectively inhibited inflammatory cell influx into the lung and attenuated AHR to methacholine provocation. Tralokinumab also inhibited antigen-induced pulmonary inflammation and AHR in an experimental model of allergic airway disease in cynomolgus monkeys.

Toxicology studies were conducted in cynomolgus monkeys following single and repeated intravenous (IV) and subcutaneous (SC) doses of tralokinumab. Following multiple IV doses of up to 100 mg/kg/week tralokinumab (longest administration schedule was weekly for 26 weeks), there were no local or systemic dose-limiting toxicities and a no-observed-adverse-effect-level of 100 mg/kg/week was identified. Repeated SC dose studies in cynomolgus monkeys showed no local or systemic effects when administered as 4-weekly SC doses up to 225 mg/injection or as 13-weekly doses up to 300 mg/injection. No adverse effects were noted in a pilot embryo-foetal development toxicity study and in a pre- and post-natal development study following the highest dose tested (100 mg/kg IV).

1.4 Summary of Clinical Experience

Seven clinical studies have been completed with tralokinumab in asthma and one study is ongoing. These include 5 completed Phase 1 studies (Studies CAT-354-0401, CAT-354-0602, CAT-354-0703, MI-CP224, and CD-RI-CAT-354-1054), 2 completed Phase 2a studies (Studies CAT-354-0603 and MI-CP199), and 1 ongoing Phase 2b study (Study CD-RI-CAT-354-1049).

The largest study completed to date, Study MI-CP199, was a Phase 2a study in which tralokinumab (150, 300, or 600 mg) or placebo was administered as a SC injection every 2 weeks (Q2W) for 3 months to 194 adult patients with uncontrolled, moderate-to-severe, persistent asthma requiring treatment with appropriate asthma controller medication. The results of this study (Piper et al, 2013) demonstrated a clinical effect with the addition of SC tralokinumab to standard asthma controller medications. An increase in pre-bronchodilator forced expiratory volume in one second (FEV₁) was observed at the first scheduled visit (2 weeks) after first dose of tralokinumab. At Day 92 (Week 13), the mean increase from baseline FEV₁ was 0.063 L (4.3%) in the placebo group versus 0.210 L (12.5%) in the combined tralokinumab group (150, 300, and 600 mg; p = 0.072). Across the majority of study time points, the magnitude of the increase in FEV_1 was similar in the 300 and 600 mg tralokinumab groups, while smaller improvements were observed in the 150 mg tralokinumab group. In addition, increases from baseline in office peak expiratory flow (PEF) and forced vital capacity, and a reduction in the requirement for the use of additional short-acting \beta2-agonist (SABA) were also observed in this study. Nearly 95% of the patients completed treatment as planned. The majority of treatment-emergent adverse events (TEAEs) were mild or moderate in severity, and there was a higher frequency of severe and serious TEAEs in the placebo group compared to the combined tralokinumab group. The most frequently reported TEAEs (incidence > 5%) in the combined tralokinumab group were asthma, headache, nasopharyngitis, and bacteriuria; the most frequently reported TEAEs (incidence > 5%) in the placebo group were nasopharyngitis, asthma, decreased neutrophil count, decreased lymphocyte count, and bronchitis. In addition, there were no confirmed anti-drug antibodies (ADA) to tralokinumab in any patient.

Study CD-RI-CAT-354-1049 is an ongoing Phase 2b, randomized, double-blind, placebocontrolled, parallel-arm, multicenter study to evaluate the efficacy and safety of two SC treatment regimens of tralokinumab (300 mg as 2 SC injections Q2W for 50 weeks or 300 mg as 2 SC injections Q2W for 12 weeks followed by every 4 weeks [Q4W] for 38 weeks) in adult patients with uncontrolled, severe asthma requiring high-dose ICS and LABA with or without additional controller medications. Recruitment to this study is complete and interim data analysis is ongoing.

In addition to asthma, tralokinumab is also being studied for other indications, including idiopathic pulmonary fibrosis and ulcerative colitis. Further information and a full list of citations can be found in the IB.

1.5 Rationale for Conducting the Study

There is an unmet medical need for new therapies for use in subjects unable to gain asthma control using standard asthma controller medications. In Study MI-CP199, treatment with tralokinumab showed evidence of an increase in FEV_1 compared with placebo and an acceptable safety profile; therefore, further study of tralokinumab as a potential therapeutic asthma-controller therapy is warranted.

A target dose of 300 mg tralokinumab administered as 2×1 mL SC injections has been established. Development of a device to support large volume delivery of tralokinumab (by large volume bolus injector or large volume autoinjector) is planned to enable the target dose to be delivered by a single injection rather than 2 individual injections. For this to be feasible, the pharmacokinetic (PK) profile of 300 mg tralokinumab when delivered via different regimens (ie, 2 injections versus 1 injection) should be equivalent and injections of the larger injection volumes (2 mL) must be tolerable for the subject. However, some evidence suggests that larger injection volumes may be associated with a higher incidence of injection site reactions, particularly increased pain intensity (Jorgensen et al, 1996). This is likely due to associated increased SC tissue pressure, which in turn may be influenced by the injection flow rate. The relationship between these variables (injection volume, injection flow rate, and local injection site tolerability) for tralokinumab is currently unknown.

The aim of the present study is to evaluate the PK and tolerability of 300 mg tralokinumab when administered SC by a single larger volume injection of 2 mL at different flow rates compared to that observed with the current method of administration (2×1 mL injections). The data gathered from this exploratory study is expected to characterize the relationship between injection volume, flow rate, and local injection site tolerability of tralokinumab, and the subsequent effect of changes in injection volume and flow rate on the observed PK for the molecule. This information will be used to optimize the design specifications for the future delivery device and to plan future studies.

The primary hypothesis to be tested is that delivery of a single 2 mL SC injection of 300 mg tralokinumab at different flow rates has no significant effects on its PK profile compared to delivery as 2×1 mL injections. Therefore, the effect of the delivery of a single 2 mL SC injection via different flow rates on the observed PK will be primarily evaluated. The tolerability of delivery of a single 2 mL SC injection of 300 mg tralokinumab at different flow rates by recording local injection site reactions as well as injection site pain intensity and injection site pruritus.

With respect to safety, in clinical studies completed to date, tralokinumab was adequately tolerated. A number of potential risks have been identified that are described in the current IB and measures are in place in this study to protect participating subjects as follows:

- Close monitoring of subjects during the study
- One acute hypersensitivity reaction, characterized by increased wheezing, shortness of breath, and facial pruritus, was reported in an asthmatic subject following the first IV infusion of tralokinumab (10 mg/kg) in Study CAT-354-0603. However, in Studies MI-CP199, no hypersensitivity reactions were reported following repeat SC dosing. As a precautionary measure in this study, subjects will be monitored closely during the post-dosing period. Vital signs will be taken immediately after administration of investigational product and 10, 30, 60 minutes, and 4 and 8 hours thereafter. Discharge will be at the discretion of the investigator. There will be 7 subsequent study site visits in the 21-day period post-injection and a further 2 visits through the end of the Follow-up Period.
- Subjects will be monitored for both clinical manifestations that may be associated with the development of specific antibodies to tralokinumab and for the presence of such antibodies
- Neutralization of IL-13 might theoretically cause a worsening of parasitic infestation, in particular, prevention of expulsion of gastrointestinal worms (Bell, 1996) and therefore, subjects either with untreated systemic helminth parasitic infestations or at significant increased risk of parasitic infestation will be excluded from participating in the study
- Subjects with a history of tuberculosis (TB) requiring treatment within the 12 months prior to the screening visit will be excluded from participating in the study
- Subjects with a history of a clinically significant infection requiring antibiotic therapy or antiviral medication from 30 days prior to screening will be excluded from the study

In conclusion, previous clinical experience with tralokinumab shows no major safety or tolerability concerns and appropriate measures have been instituted in this study to protect subjects from possible risks that have been previously identified and to closely monitor each subject. The current risk/benefit ratio is favorable and justifies the administration of tralokinumab for the purposes of achieving the objectives of this study.

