4.1.3 Exclusion Criteria

Any of the following would exclude the subject from participation in the study:

- 1. Concurrent enrollment in another clinical study where the subject is receiving an investigational product
- 2. Individuals who are legally institutionalized
- 3. Receipt of any marketed or investigational biologic agent within 4 months or 5 half-lives prior to screening, whichever is longer
- 4. Receipt of any investigational nonbiologic agent within 3 months or 5 half-lives prior to screening, whichever is longer

- 5. Known history of allergy or reaction to any component of the investigational product formulation
- 6. History of anaphylaxis following any biologic therapy
- 7. Current use of regular pain-modifying, anti-depressant, anxiolytic, or hypnotic medication
- 8. History of thrombocytopenia or bleeding disorder or use of anticoagulants such as warfarin, heparin/low molecular weight heparin, thrombin inhibitors (dabigatran and others), or factor Xa inhibitors (rivaroxaban, apixaban, and others)
- 9. Any pathology on abdomen that could potentially interfere with study outcome or interpretation of results
- 10. History of chronic alcohol or drug abuse within 12 months prior to screening, or any condition associated with poor compliance as judged by the investigator
- 11. Pregnant or breastfeeding women
- 12. Any active medical or psychiatric condition or other reason which, in the opinion of the investigator or medical monitor, may compromise the safety of the subject in the study or interfere with evaluation of the investigational product or reduce the subject's ability to participate in the study
- 13. Any clinically relevant abnormal findings in physical examination, ECG, vital signs, hematology, clinical chemistry, or urinalysis during screening, which in the opinion of the investigator or medical monitor may compromise the safety of the subject in the study or interfere with evaluation of the investigational product or reduce the subject's ability to participate in the study
- 14. History of any known immunodeficiency disorder or use of immunosuppressive medication
- 15. History of a clinically significant infection requiring antibiotics or antiviral medication from 30 days prior to screening, up to and including Day 1
- 16. Diagnosis of a helminth parasitic infection within 6 months prior to screening that has not been treated with, or has failed to respond to, standard of care therapy

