- 17. History of cancer, except for basal cell carcinoma or in situ carcinoma of the cervix treated with apparent success with curative therapy ≥ 12 months prior to screening or other malignancies treated with apparent success with curative therapy ≥ 5 years prior to screening
- 18. Tuberculosis requiring treatment within the 12 months prior to the screening visit
- 19. Positive hepatitis B surface antigen or hepatitis C virus antibody serology. Subjects with a history of hepatitis B vaccination without history of hepatitis B are allowed to enroll.
- 20. A positive human immunodeficiency virus (HIV) test at screening or subject taking antiretroviral medications, as determined by medical history and/or subject's verbal report
- 21. Evidence of active liver disease, including jaundice or aspartate transaminase (AST), alanine transaminase (ALT), or alkaline phosphatase greater than twice the upper limit of normal (ULN)
- 22. Major surgery within 8 weeks prior to Visit 1, or planned in-patient surgery or hospitalization during the study period

23. Receipt of live attenuated vaccines 30 days prior to screening, up to and including Day 1

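### Section 1.5 says volunteers at raised risk of parasitic infestation will be excluded, but no eligibility criterion names them (minor, safety)

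*Protocol*

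**What the plan says.** Section 1.5 of the Protocol reviews the known and theoretical risks of tralokinumab and states that "measures are in place in this study to protect participating subjects as follows". One item in the list that follows concerns parasites. Because blocking IL-13 could in theory hinder the expulsion of gut worms, "subjects either with untreated systemic helminth parasitic infestations or at significant increased risk of parasitic infestation will be excluded". The same list also promises to exclude volunteers with recently treated tuberculosis and those with a recent clinically significant infection. The section ends by relying on these measures to call the risk/benefit balance favorable.

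The operative rules are in Sections 4.1.2 and 4.1.3. The exclusion list opens with "Any of the following would exclude the subject from participation in the study". Its only parasite entry is criterion 16, which begins "Diagnosis of a helminth parasitic infection within 6 months prior to screening that has not been treated with, or has failed to respond to" and ends by naming standard-of-care therapy. Criterion 12 is a general provision. Besides current physical or mental illness, it can be applied for any "other reason which, in the opinion of the investigator or medical monitor, may compromise the safety of the subject in the study". Criterion 14 covers "History of any known immunodeficiency disorder or use of immunosuppressive medication".

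**The concern.** The rationale makes a categorical promise about two separate groups, and the eligibility lists carry over only one. Section 4.1.4 describes the screening evaluations as assessing the inclusion and exclusion criteria, so a site will check volunteers against those lists and not against the rationale in Section 1.5.

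A volunteer with heavy exposure to helminths but no diagnosis falls outside criterion 16. This is the kind of person the at-risk wording would catch. Such a volunteer could meet every listed criterion and be dosed, although Section 1.5 says otherwise. The safety argument put to the ethics committee would then claim a safeguard that the criteria do not deliver.

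**Working it through.** No sample size, power or other computed figure is involved. The check compares Section 1.5 with all the eligibility criteria and with the screening schedule.

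**Step 1. Match each promised exclusion to a criterion.**

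| Group excluded in Section 1.5 | Criterion in Section 4.1.3 | Match |
|---|---|---|
| Untreated systemic helminth infestation | 16 | Named, but limited to a diagnosis in the 6 months before screening |
| Raised risk of parasitic infestation | none | Not named |
| Tuberculosis treated in the past 12 months | 18: "Tuberculosis requiring treatment within the 12 months prior to the screening visit" | Named |
| Recent clinically significant infection | 15: "History of a clinically significant infection requiring antibiotics or antiviral medication from 30 days prior to screening, up to and including Day 1" | Named |

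Named: 3. Not named: 1. Total: 3 + 1 = 4. The numbering runs without a gap from 1 to 10 and from 1 to 23, so nothing suggests that a criterion was lost from the text.

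**Step 2. Search all the criteria for the missing group.** 10 inclusion + 23 exclusion = 33 criteria, and 0 of 33 name risk of parasitic infestation.

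**Step 3. Ask which criteria could reach the group indirectly.**

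- Criterion 12 could, if the investigator or medical monitor judges the volunteer's safety to be compromised. It permits exclusion, whereas Section 1.5 promises it.
- Criterion 13 also rests on judgment and needs an abnormal screening finding, which exposure alone need not produce.
- Criterion 14 may overlap slightly, but it concerns immune status and not exposure.

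**Step 4. Ask whether screening would bring the risk to light.** Table 4.2.1-1 lists no parasite test or exposure assessment. The medical history in Section 4.3.2.1 covers gastrointestinal, immunologic and drug history among other systems, but does not ask about exposure.

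**Step 5. Count the checks that use these lists.** Eligibility is verified once at Visit 1 (Table 4.2.1-1) and twice at Visit 2, on Day -1 and Day 1 (Table 4.2.2-1): 1 + 2 = 3 times. Section 4.6.1 places a confirmation of eligibility on Day 1 as the first step of randomization. Repeating the check does not help, because each one uses the same criteria.

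**The case against.** The strongest reply is that this is missing wording and not a conflict of instructions. No criterion admits at-risk volunteers, and criterion 12 is wide enough to exclude them. Section 1.5 gives no definition, threshold or test for raised risk, so applying it would take clinical judgment anyway. Copying the phrase into criterion 16 undefined would gain little more than a prompt to ask. Section 4.1.4 mentions the criteria only in passing and does not say that the rest of the Protocol has no bearing on eligibility. Under Section 6.1, site staff are trained on the requirements of the whole Protocol. The mechanism is theoretical, exposure is a single dose at one site, and no harm is shown.

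Much of this stands, and it is why the point is minor. It also shows that a new criterion needs a definition to be worth adding. It does not close the gap: discretion to exclude is weaker than a statement that a group will be excluded, and nothing at screening prompts the investigator to use that discretion for this reason.

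It is also fair to say that counting three of four groups as matched is generous. Criterion 16 has a 6-month limit that Section 1.5 lacks, so the match for untreated infestation is partial. That does nothing to supply the missing at-risk criterion.

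**Conclusion.** The concern holds as a minor internal inconsistency on eligibility. One of the four groups that Section 1.5 says are excluded has no criterion naming it, and the only realistic route to excluding it is the discretionary criterion 12. A site applying the lists as written could dose such a volunteer.

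The practical effect is likely to be small, with one dose each in 60 healthy volunteers and a risk the Protocol itself calls theoretical. How many volunteers might be affected is unknown, because the document gives no prevalence and the site location is blank. The primary endpoint, the power calculation and the planned analyses are untouched. The conclusion assumes that sites screen from the listed criteria, as Section 4.1.4 and the schedule tables indicate.

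**What to change.** Extend exclusion criterion 16, or add a new criterion, to cover volunteers at raised risk of parasitic infestation. The sponsor's clinical team should supply a working definition of that risk so that the criterion does more than repeat criterion 12. Add one exposure question to the screening medical history to check it.

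If the sponsor did not mean to exclude this group, the alternative is to remove the phrase from Section 1.5 so that the rationale claims only what the criteria require. Adding the criterion is the better choice for safety.

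The cost is one line in the exclusion list and one history question, made by protocol amendment, and possibly a few more screen failures. Nothing changes in the randomization, sample size or analysis.
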